5.2 Sample Size

This phase III clinical trial is designed to determine a statistically significant difference in PFS by IRC between PM01183 and a control arm with PLD or topotecan in ovarian cancer patients with platinum-resistant disease.

Patients will be randomized to receive PM01183 given as 3.2 mg/m² (Arm A) or either topotecan or PLD (Arm B).

The prospective assumptions are a 30% reduction in the relative risk of progression or death (HR=0.7) to be achieved with the experimental arm (PM01183), at a one-sided 2.5% significance level with at least 90% power, following exponential distributions and fulfilling the proportional hazard assumption. Median PFS with control arm is expected to be around 3.5 months. It is forecasted that an observed HR of approximately 0.8 will have enough power to reject the null hypothesis (HR=1).

Approximately 420 patients with platinum resistant ovarian cancer will be necessary to stratify and randomize at a 1:1 ratio over 18 months (~23 patients/month). The required 332 PFS events are expected to occur around six months after randomization of the last patient. Therefore, the IDMC meeting after the IRC review to test PFS is expected to occur about one year after randomization of the last patient.

With the prospective assumptions above mentioned, about 175 PFS events are expected in the control arm and 157 in the PM01183 treatment arm.

The IDMC will review the results of the analyses. The IRC will determine the patient's best response and assign the date of objective response or progression/censoring according to the RECIST v.1.1.

5.2.1 *Futility Analysis*

A futility analysis will be performed when 210 patients are recruited (i.e., ~105 patients enrolled in each arm). The recruitment will not be put on hold.

In the futility analysis, the sponsor will make no claim of efficacy, consequently this futility analysis and the final analysis to reject the null hypothesis ($HR=1$) are planned; the significance level will be determined by the actual number of observed events by IR. To maintain scientific integrity, type II error will be controlled by a spending function defined by O'Brien-Fleming boundaries. Following the prospective assumptions, the interim analysis will occur at less than one year after start of recruitment. At this moment, with the available information collected after balancing efficacy and safety, the IDMC might recommend stopping the trial.

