All variables with a good percentage of valid cases (approximately \geq 90%) will be included in the multivariate analysis. Within the multivariate stepwise Logistic/Cox regression analysis, the chosen significance level for entering an explanatory variable into the model will be 0.05 (for all variables not in the model, the one with the smallest p-value will be entered if the p-value is less than or equal to the specified significance level). The significance level for removing an explanatory variable from the model will be 0.05 (for all variables in the model, the one with the largest p-value will be removed if the p-value exceeds the specified significance level). The parameter estimates, hazard ratios/odds ratios and p-values of the variables retained in the model will be presented.

Forest plots for PFS and OS summarizing main results, stratification and factors/covariates used in multivariate analyses will be plotted⁽²⁾.

Median follow-up (FU) time for PFS and OS will be calculated in the descriptive way, only taking into account the censored values and using the Kaplan-Meier method for reversing the censoring values as described by Parmar⁽³⁾.

Concordance between IRC and IA PFS assessments will be evaluated by means of Kaplan-Meier curves. Forest plots for response will also be performed adapting them to show relevant information (e.g. percentages will be shown instead of medians).

Sensitivity analyses for different PFS censoring will be performed. The following approaches will be calculated: 1) Date of progression based on scheduled time instead of recorded date (e.g. if progression occurs in the eleventh week and assessment would have to be done in the eighth week then the expected date is used instead of the actual date); 2) First date of progression combining IRC and IA assessments (e.g. the lowest date between IRC and IA is used); and 3) Date of progression moved to the prior tumor assessment date (e.g. if progression has not been documented in the second assessment and is documented in the third assessment then progression date is moved to the second assessment).

Proportional hazard assumption for PFS and OS will be checked by means of a Cox regression including treatment and its interaction with survival time⁽⁴⁾. In case of strong rejection of proportionality, then restricted mean survival estimates will also be calculated in addition to HR^(5,6).

Main summary of efficacy analyses

Endpoint	Population	Statistics

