8.9 Subgroup Analyses

Subgroup analyses implemented a posteriori based on clinically findings will have an exploratory nature.

Some exceptions are the upfront preplanned exploratory analyses, such as efficacy subgroup analyses based on comparison of PM01183 with PLD or topotecan, subgroup analyses for stratification factors, and the analysis of the subset of patients who received a platinum compound as first subsequent treatment.

Pre-specified safety subgroup analyses are: by age (<65 years-old vs. \geq 65 years-old), by race (white vs. other), by number of prior chemotherapy lines (1-2 vs. 3 lines) and by geographical area (USA vs. Europe vs. rest of the world).

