11.3 Efficacy Analysis

Efficacy analysis will be carried out on the ITT population.

Table 11.3.1.1 PFS by IRC (primary analysis)

Variable	Stratification factors	p-value*
Treatment arm (main analysis)	Actual values	
Treatment arm (sensitivity)	Values reported for randomization	

*Stratified log rank test.

Progression-free survival by IRC

Table 11.3.1.2 Median FU for PFS by IRC

		Total (PM01183 and Control)
Follow-up (descriptive way)		Median (range)
Follow-up (reverse censoring method)		Median (95%CI)

Table 11.3.1.3 PFS by IRC

	PM01183	Control	Parameter	p-value
N				
Events				
Censored				
Median PFS (95% CI)			Log-Rank: HR (95% CI) :	LR: HR:
PFS at 6 months (95% CI)			Diff:	
PFS at 12 months (95% CI)			Diff:	

Kaplan Meier plot (Figure 11.3.1.3) will be shown too.

Table 11.3.1.4 Multivariate analysis of PFS by IRC (Stratification factors and treatment arm)

Analysis of maximum likelihood estimates								
Variable label	Variable values	DF	Parameter estimate	Standard error	Chi-square	Pr > ChiSq	Hazard ratio	95% Hazard ratio confidence limits

Table 11.3.1.5 Multivariate analysis of PFS by IRC

Analysis of maximum likelihood estimates								
Variable label	Variable values	DF	Parameter estimate	Standard error	Chi-square	Pr > ChiSq	Hazard ratio	95% Hazard ratio confidence limits

(see list of covariates in section 6.2).

Table 11.3.1.6 Proportional hazard assumption and restricted mean survival for PFS by IRC

Variable	PM01183	Control	Interaction p-value
Restricted mean survival [*]			

*It will be calculated if proportional hazard assumption is not met.

A forest plot (Figure 11.3.1.7) summarizing main results, stratification factors and covariates in terms of PFS by IRC will be plotted.

Progression-free survival by IA

Table 11.3.1.8 PFS by IA (Stratified log rank test)

Variable	Stratification factors	p-value*
Treatment arm (main analysis)	Actual values	
Treatment arm (sensitivity)	Values reported for randomization	

*Stratified log rank test.

Table 11.3.1.9 Median FU for PFS by IA

	Total (PM01183 and Control)
Follow-up (descriptive way)	Median (range)
Follow-up (reverse censoring method)	Median (95%CI)

Table 11.3.1.10 PFS by IA

	PM01183	Control	Parameter	p-value
N				
Events				
Censored				
Median PFS (95% CI)			Log-Rank: HR (95% CI) :	LR: HR:
PFS at 6 months (95% CI)			Diff:	
PFS at 12 months (95% CI)			Diff:	

Kaplan Meier plot (Figure 11.3.1.10) will be shown too.

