Reason	IRC				IA			
	PM01183		Control		PM01183		Control	
	N	%	N	%	N	%	N	%
Target lesion								
Non-target lesion								
Death due to malignant disease								
Other*								

(*)Please specify.

Table 11.3.1.44 Censoring reason by IRC/IA

Reason	IRC				IA			
	PM01183		Control		PM01183		Control	
	N	%	N	%	N	%	N	%
Free of progression last tumor assessment								
Subsequent therapy before documented progression								
Not treated								
Other*								

(*)Please specify.

Subgroup analyses

Forest plots summarizing main results, stratification factors and covariates for the comparison between PM01183 and PLD will be plotted.

- Figure 11.3.1.45 PFS by IRC (PM01183 vs PLD)
- Figure 11.3.1.46 PFS by IA (PM01183 vs PLD)
- Figure 11.3.1.47 OS (PM01183 vs PLD)
- Figure 11.3.1.48 RR by IRC (PM01183 vs PLD)
- Figure 11.3.1.49 RR by IA (PM01183 vs PLD)
- Figure 11.3.1.50 DR by IRC (PM01183 vs PLD)
- Figure 11.3.1.51 DR by IA (PM01183 vs PLD)
- Figure 11.3.1.52 CA125 by IRC (PM01183 vs PLD)

Forest plots summarizing main results, stratification factors and covariates for the comparison between PM01183 and Topotecan will be plotted.

- Figure 11.3.1.53 PFS by IRC (PM01183 vs Topotecan)
- Figure 11.3.1.54 PFS by IA (PM01183 vs Topotecan)
- Figure 11.3.1.55 OS (PM01183 vs Topotecan)
- Figure 11.3.1.56 RR by IRC (PM01183 vs Topotecan)
- Figure 11.3.1.57 RR by IA (PM01183 vs Topotecan)
- Figure 11.3.1.58 DR by IRC (PM01183 vs Topotecan)
- Figure 11.3.1.59 DR by IA (PM01183 vs Topotecan)
- Figure 11.3.1.60 CA125 by IRC (PM01183 vs Topotecan)

Forest plots summarizing main results, stratification factors and covariates for the comparison between PM01183 and Control arm selecting patients who received as first subsequent therapy a platinum line will be plotted.

- Figure 11.3.1.61 PFS by IRC (PM01183 vs Control)
- Figure 11.3.1.62 PFS by IA (PM01183 vs Control)
- Figure 11.3.1.63 OS (PM01183 vs Control)

- Figure 11.3.1.64 RR by IRC (PM01183 vs Control)
- Figure 11.3.1.65 RR by IA (PM01183 vs Control)
- Figure 11.3.1.66 DR by IRC (PM01183 vs Control)
- Figure 11.3.1.67 DR by IA (PM01183 vs Control)
- Figure 11.3.1.68 CA125 by IRC (PM01183 vs Control)

In the forest plots continuous variables not categorized in the definition will be coded into two categories taking as reference the median value, below or equal the median value and above the median value.

Characteristics of responders

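### The exploratory efficacy forest plots cover up to 38 factors, but no treatment-by-factor interaction estimate is prespecified for them

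*SAP*

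**What the plan says.** SAP 6.2 commits to the display: "Forest plots for PFS and OS summarizing main results, stratification and factors/covariates used in multivariate analyses will be plotted". It adds similar plots for response, showing percentages where the time-to-event plots show medians, which implies a summary for each level of each factor. Section 11.3 repeats the plan figure by figure. Figure 11.3.1.7, for example, is a forest plot "summarizing main results, stratification factors and covariates in terms of PFS by IRC will be plotted". The plots are repeated for PM01183 against PLD, PM01183 against topotecan, and patients whose next therapy contained platinum (Figures 11.3.1.45 to 11.3.1.68). On continuous factors, 11.3 says: "In the forest plots continuous variables not categorized in the definition will be coded into two categories taking as reference the median value".

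The list in 6.2 contains 38 factors besides treatment. This is a ceiling, because a variable enters the multivariate analysis only with roughly 90% or more valid cases.

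Interactions appear in two places. Section 6.2 lets the multivariate models include interaction terms where judged appropriate; it names none and gives no criterion. The shells have an interaction p-value column (Tables 11.3.1.6, 11.3.1.13 and 11.3.1.27), but this belongs to the proportional-hazards check, which 6.2 defines as treatment by survival time.

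Section 8.9 lists "subgroup analyses for stratification factors" among its preplanned analyses and calls those analyses exploratory.

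**The concern.** A forest plot of within-level estimates does not show directly whether the treatment effect differs between levels. That question is answered by the ratio of the two hazard ratios and its interval. Without it, readers tend to compare which intervals exclude 1. Each level has only part of the trial's events, so under a uniform effect one level will often reach that threshold and the other miss it.

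At stake is the interpretation of the exploratory results by PFI, performance status, prior lines and the other factors. A constant effect could be described as confined to one group, and a real difference would have no prespecified assessment. The protocol (3.2) left the details of the subgroup analyses to the SAP, which lists factors and figures but no method for judging whether effects differ.

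**Working it through.** **Inputs from SAP 5.2.** HR 0.70; design "at a one-sided 2.5% significance level with at least 90% power"; and "The required 332 PFS events are expected to occur around six months after randomization of the last patient". Allocation is 1:1 (SAP 5.1).

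**Reproducing the design.** Schoenfeld: 4 × (1.960 + 1.282)² / (ln 0.70)² = 331 events after rounding up, against 332 stated. Power at 332 events is 0.901. The largest observed HR that rejects is exp(−1.96 × 2/√332) = 0.806, matching the plan's approximate 0.8.

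**One level only, even split.** Suppose the true HR is 0.70 in everyone and each level has 332/2 = 166 events.

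- SE(log HR) = 2/√166 = 0.155.
- P(95% CI excludes 1 in favour of PM01183) = Φ(0.357/0.155 − 1.96) = 0.632.
- The levels contain different patients, so P(exactly one excludes 1) = 2 × 0.632 × 0.368 = 0.465. Both exclude 1 with probability 0.400, and neither with 0.135.

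**Unequal split (assumption).** The documents give no prevalences for the categorical factors. At 25/75 the levels have 83 and 249 events and probabilities 0.369 and 0.803. Then 0.369 × (1 − 0.803) + 0.803 × (1 − 0.369) = 0.580, using unrounded values.

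**Sensitivity.** Probability that exactly one level has a 95% CI excluding 1:

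| True uniform HR | 50/50 | 25/75 | 10/90 |
|---|---|---|---|
| 0.60 | 16.6% | 36.2% | 68.5% |
| 0.70 | 46.5% | 58.0% | 74.0% |
| 0.75 | 49.6% | 55.9% | 64.9% |
| 0.80 | 42.1% | 44.8% | 49.0% |

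**Number of factors.** Thirteen listed factors have no categories: age, age at diagnosis, BMI, height, weight, BSA, time since diagnosis, time since last platinum dose, sum of target diameters, CA-125, albumin, PFS on the prior line and global QoL. The SAP's median rule makes these close to 50/50. If all are plotted, the expected number showing one level only is 13 × 0.465 = 6.0 at HR 0.70. Region and prior cytoreduction have three levels, leaving at most 38 − 2 = 36 two-level factors; if all were split evenly, 36 × 0.465 = 16.7. Correlation between factors leaves these expectations unchanged, but the signals would overlap.

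**Interaction test.** Under the same uniform effect, a test at two-sided 5% flags 5% of factors: 38 × 0.05 = 1.9 per plot. In simulation (2,000,000 replicates), only about 10% of the one-level-only patterns at 50/50, and 7% at 25/75, also had interaction p < 0.05. The chance of at least one false flag among 38 independent tests is 1 − 0.95³⁸ = 0.86.

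**Power of that test.** At 50/50, SE(log ratio of HRs) = √(4/166 + 4/166) = 0.220. The observed ratio must exceed exp(1.96 × 0.220) = 1.54, or fall below 0.65, to reach p < 0.05.

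**The case against.** The other side has a good case.

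- **Interaction terms are not excluded.** SAP 6.2 permits them in models built on the same factors as the plots. A reader might infer that the plan never looks at heterogeneity; the text does not support that. It supports only that no interaction is prespecified or linked to a plot. Those models are stepwise at 0.05 and present the retained variables, so nothing ensures that an interaction is reported for every factor.
- **No reading rule is stated.** Nowhere does the SAP say that a subgroup will be judged by whether its interval excludes 1. A reader might infer that it plans to declare benefit that way; it does not. The 46.5% describes a common way of reading such plots.
- **The analyses are exploratory.** Section 8.9 says so, and no claim or alpha depends on them.
- **The secondary objective is narrower.** It concerns PM01183 against PLD or topotecan, not subgroups in general, although 11.3 reports that comparison through the same kind of covariate forest plots.
- **Interaction tests have their own faults.** They are weak here and, over many factors, will produce chance flags.

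All five points stand, and they limit the severity. They do not supply the estimate of differential effect that the plots lack.

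**Conclusion.** The point holds as a minor one: a cheap improvement to exploratory figures. The one-level-only rate of 46.5% (50/50) or 58% (25/75, assumed) against 5% for an interaction test applies to PFS, 332 events, a uniform true HR of 0.70 and two-level factors, for a reader who uses the interval-excludes-1 rule. It depends on the true HR: at 0.60 with an even split it falls to 16.6%.

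Two stronger conclusions may tempt a reader. One is that about half of all factors in every efficacy plot will mislead. The calculation does not extend unchanged to OS, response, the three-level factors or the PLD-only and topotecan-only plots, which have fewer events, and the categorical splits are unknown. The other is that the trial's error control is damaged. The stratified log-rank test of PFS by IRC does not depend on these plots.

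**What to change.** In SAP 6.2 and in Figures 11.3.1.7, 11.3.1.14, 11.3.1.28, 11.3.1.32 and 11.3.1.38, with the matching PFS, OS and response figures in the subgroup set (11.3.1.45–49, 53–57 and 61–65):

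- For each factor, add the ratio of HRs (ORs for response) with its 95% CI and the interaction p-value. Take these from a Cox model with treatment, factor and their interaction, stratified by the randomisation factors, or from a logistic model adjusted for them. Where the factor is itself a stratification factor, the strata absorb its main effect in the Cox model.
- Fit continuous factors on the continuous scale and keep the median split for display.
- State that a differential effect is described only on the interaction estimate; that the tests are exploratory and unadjusted, with about 2 of 38 expected by chance per plot; that a non-significant result is not proof of consistency; and how many factors were examined.

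The cost is SAP wording and extra plot columns, with no new data. The price in chance findings is real: 5 × 38 = 190 tests on the five main plots give about 190 × 0.05 = 9.5 flags with no heterogeneity, and all 20 plots give 20 × 1.9 = 38. The exploratory label must therefore appear with the figures.

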6 STATISTICAL METHODOLOGY FOR EFFICACY

6.1 *Efficacy Definitions*

Primary endpoint.

Progression-free survival (PFS) by IRC is defined as the time from the date of randomization to the date of documented progression per RECIST v.1.1 or death (regardless of the cause of death). If the patient receives further antitumor therapy or is

lost to follow-up before PD, PFS will be censored at the date of last tumor assessment before the date of subsequent antitumor treatment.

Irrespectively of treatment arm, radiological and clinical tumor assessment will be performed symmetrically at baseline and every eight weeks from randomization until evidence of PD is found. Patients who finish treatment without radiological PD will continue with the tumor assessments every eight weeks (\pm two weeks) from randomization until PD, start of a new antitumor therapy, death or date of study termination (clinical cut-off), whichever occurs first.

After radiological PD is documented or a new antitumor therapy is started, patients will be followed for survival at least every three months (\pm two weeks) from the end-of-treatment visit until death or date of study termination, whichever occurs first. Once the whole recruitment is completed, the 3-month follow-up for patients who discontinue treatment due to PD will be performed according to calendar time. Follow-up for survival, after radiological PD is documented or new therapy is started, may be made by telephone calls to the investigational sites.

The date of clinical and/or radiological PD and the date of death will be registered and documented as appropriate.

Copies of CT scans, MRIs and any other documented means to evaluate tumor response or progression should be available for external radiological review by an IRC. The IRC will determine the patient's best response, and assign the date of objective response or progression/censoring according to RECIST v.1.1.

Crossover after treatment discontinuation from Arm B to Arm A is not allowed.

Secondary endpoints.

Progression-free survival (PFS) by IA will be calculated using the same methodology as explained above for IRC assessment but following investigator assessments.

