Table 11.3.1.11 Multivariate analysis of PFS by IA (Stratification factors and treatment arm)

Analysis of Maximum Likelihood Estimates								
Variable label	Variable values	DF	Parameter estimate	Standard error	Chi-square	Pr > ChiSq	Hazard ratio	95% Hazard ratio confidence limits

Table 11.3.1.12 Multivariate analysis of PFS by IA

Analysis of Maximum Likelihood Estimates								
Variable label	Variable values	DF	Parameter estimate	Standard error	Chi-square	Pr > ChiSq	Hazard ratio	95% Hazard ratio confidence limits

(see list of covariates in section 6.2).

Table 11.3.1.13 Proportional hazard assumption and restricted mean survival for PFS by IA

Variable	PM01183	Control	Interaction p-value
Restricted mean survival*			

*It will be calculated if proportional hazard assumption is not met.

A forest plot (Figure 11.3.1.14) summarizing main results, stratification factors and covariates in terms of PFS by IA will be plotted.

Table 11.3.1.15 Time to disease assessments

Disease assessment	Treatment arm	n	Median (days)	Wilcoxon p-value
1	PM01183			
	Control			
2	PM01183			
	Control			
...	PM01183			
	Control			

-ITT population, Kaplan Meier plot (Figure 11.3.1.15) will be shown too.

Concordance PFS IRC and PFS IA

Table 11.3.1.16 Concordance PFS

	PM01183 (IRC)	PM01183 (IA)	Control (IRC)	Control (IA)	Parameter	p-value
N						
Events						
Censored						
Median PFS (95% CI)					Log-Rank:	LR:
PFS at 6 months (95% CI)						
PFS at 12 months (95% CI)						

Kaplan Meier plot (Figure 11.3.1.16) will be shown too.

Sensitivity PFS analyses

-Date of progression based on scheduled time instead of recorded date.

Table 11.3.1.17 PFS based on scheduled time by IRC

	PM01183	Control	Parameter	p-value
N				
Events				
Censored				
Median PFS (95% CI)			Log-Rank: HR (95% CI) :	LR: HR:
PFS at 6 months (95% CI)			Diff:	
PFS at 12 months (95% CI)			Diff:	

Kaplan Meier plot (Figure 11.3.1.17) will be shown too.

Table 11.3.1.18 PFS based on scheduled time by IA

	PM01183	Control	Parameter	p-value
N				
Events				
Censored				
Median PFS (95% CI)			Log-Rank: HR (95% CI) :	LR: HR:
PFS at 6 months (95% CI)			Diff:	
PFS at 12 months (95% CI)			Diff:	

Kaplan Meier plot (Figure 11.3.1.18) will be shown too.

-First date of progression combining IRC and IA assessments

Table 11.3.1.19 PFS based on first date of progression

	PM01183	Control	Parameter	p-value
N				
Events				
Censored				
Median PFS (95% CI)			Log-Rank: HR (95% CI) :	LR: HR:
PFS at 6 months (95% CI)			Diff:	

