PR					
SD					
PD					
Unknown*					
CR+PR; n (%) and binomial exact 95% confidence interval					

(*) Including NE, non-responders and insufficient data available.

Table 11.3.1.30 Multivariate analysis of response rate by IRC (Stratification factors and treatment arm)

Table 11.3.1.31 Multivariate analysis of response rate by IRC

(See list of covariates in section 6.2).

A forest plot (Figure 11.3.1.32) summarizing main results, stratification factors and covariates in terms of response by IRC will be plotted.

A waterfall plot (Figure 11.3.1.33) describing the best variation of the sum of target lesions during the treatment will be plotted.

Table 11.3.1.34 DR by IRC

	PM01183	Control	Parameter	p-value
N				
Events				
Censored				
Median DR (95% CI)			Log-Rank: HR (95% CI) :	LR: HR:

Objective response and duration of response by IA

Table 11.3.1.35 Response rate by IA

Response	PM01183		Control		p-value
	N	%	N	%	
CR					
PR					
SD					
PD					
Unknown*					
CR+PR; n (%) and binomial exact 95% confidence interval					

(*) Including NE, non-responders and insufficient data available.

Table 11.3.1.36 Multivariate analysis of response rate by IA (Stratification factors and treatment arm)

Table 11.3.1.37 Multivariate analysis of response rate by IA

Analysis of maximum likelihood estimates								
Variable label	Variable values	DF	Estimate	Standard error	Wald chi-square	Pr > ChiSq	Odds ratio estimate	95% Wald confidence limits

(See list of covariates in section 6.2).

A forest plot (Figure 11.3.1.38) summarizing main results, stratification factors and covariates in terms of response by IA will be plotted.

A waterfall plot (Figure 11.3.1.39) describing the best variation of the sum of target lesions during the treatment will be plotted.

Table 11.3.1.40 DR by IA

	PM01183	Control	Parameter	p-value
N				
Events				
Censored				
Median DR (95% CI)			Log-Rank: HR (95% CI) :	LR: HR:

CA-125 Objective response

Table 11.3.1.41 CA-125 response rate

Response	PM01183		Control		p-value
	N	%	N	%	
CR					
PR					
SD					
PD					
Unknown*					
CR+PR; n (%) and binomial exact 95% confidence interval					

(*) Including NE, non-responders and insufficient data available.

Table 11.3.1.42 CA-125 response rate (excluding UK category)

Response	PM01183		Control		p-value
	N	%	N	%	
CR					
PR					
SD					
PD					
CR+PR; n (%) and binomial exact 95% confidence interval					

Progression and censoring reasons by IRC/IA

Table 11.3.1.43 Progression type by IRC/IA

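### The IRC/investigator PFS concordance output (SAP Table 11.3.1.16) carries a log-rank p-value with no named comparison; no reading of it measures agreement, and no table counts discordant patients by arm

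*SAP*

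**What the plan says.** SAP 6.2 gives one sentence on the method: "Concordance between IRC and IA PFS assessments will be evaluated by means of Kaplan-Meier curves". No test is attached to it.

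The shell headed "Table 11.3.1.16 Concordance PFS" (SAP 11.3) has columns for PM01183 (IRC), PM01183 (IA), Control (IRC) and Control (IA). Its rows are N, events, censored, median PFS, and 6- and 12-month PFS, and a Kaplan-Meier plot goes with it. Beside the median is a single log-rank cell with a single p-value. There is no hazard ratio, and no note of which groups are compared or whether the test is stratified.

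Elsewhere, 6.2 plans unstratified log-rank tests as supportive analyses, and its summary table lists that test for PFS by IRC/IA. IA PFS is a secondary endpoint that "will be calculated using the same methodology as explained above for IRC assessment but following investigator assessments" (SAP 6.1). Scans continue "every eight weeks from randomization until evidence of PD is found". Other outputs that use both readers are:

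- Tables 11.3.1.3 and 11.3.1.10: arm comparison within each reader
- Table 11.3.1.19: PFS on the earlier of the two readers' dates
- Table 11.3.1.43: progression type
- Table 11.3.1.44: censoring reason
- ICH listing 16.2.6: PFS and event status under both readers, patient by patient

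**The concern.** Agreement is a property of pairs: for one patient, did both readers call progression, and at the same assessment? Kaplan-Meier curves and log-rank tests use only the distribution in each column, so they cannot answer that.

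The trial is open-label, so whether investigators date progression differently from the IRC in one arm is what a concordance analysis should bring out. As the shell stands, the programmer must choose the comparison, possibly after seeing data. A non-significant IRC-versus-IA p-value could be reported as the readers agreeing. A significant four-group p-value could be reported as the readers differing, when it reflects only a treatment effect.

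**Working it through.** **Design figure.** Events for HR 0.70, one-sided 2.5%, 90% power, 1:1: 4(1.960 + 1.282)² / (ln 0.70)² = 330.4, so 331, against the SAP's 332. Power at 332 is 90.1%. Nothing below changes this.

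**What the table can detect.** Shuffle the IA records among patients within each arm. Every curve, median, event count and log-rank p-value in Table 11.3.1.16 stays the same. In one simulated data set, agreement on event status fell from 100% to 60% (PM01183) and 79% (control) with no entry changed. This needs no assumed discordance rate.

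**Three readings of the p-value.**

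1. *IRC versus IA.* The ordinary log-rank takes the variance of the difference as if the samples were independent, 2σ². With paired records it is 2σ²(1 − ρ), and ρ is high, so the test rejects far too rarely.
2. *Four groups.* If the readers agree perfectly, every record is duplicated and the statistic is about twice the treatment chi-square (2.01 in simulation). The 3-df 5% point is 7.815, and 7.815/2 = 3.907, which is a treatment p of 0.048. It is in effect the treatment test: 91% rejection at HR 0.70 and 5.0% at HR 1, both with perfect agreement.
3. *Arm versus arm within a reader.* Valid and planned, but already in Table 11.3.1.3 (IRC) and "Table 11.3.1.10 PFS by IA".

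**Size under assumed timing discordance.** From SAP 5.2: 210 per arm, exponential PFS, control median 3.5 months, HR 0.70, 18 months' accrual plus 6. Assumed: scans every 56 days, each moved by up to 7 days; progression dated at the next scan (so observed control medians are about 4.3 months); no dropout; IA one scan later than the IRC with the stated probability; two-sided 5%; 2,000 runs for the rejection rates and hazard ratios.

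| IA later, PM01183 / control | IRC-vs-IA rejection: PM01183, control, pooled | HR by IRC, by IA | Median, PM01183 | Median, control |
|---|---|---|---|---|
| 20% / 0% | 0%, 0%, 0% | 0.701, 0.655 | 5.8 → 6.2 | 4.3 → 4.3 |
| 30% / 10% | 0%, 0%, 0% | 0.700, 0.656 | 5.8 → 6.5 | 4.3 → 4.7 |
| 30% / 30% | 0%, 0%, 0% | 0.702, 0.705 | 5.8 → 6.5 | 4.3 → 5.3 |
| 50% / 50% | 0.2%, 44%, 96% | – | – | – |

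With 2% per month dropout, events are 172 (control) and 153 (PM01183), near the SAP's 175 and 157. The first row then gives 0% rejection and hazard ratios of 0.705 and 0.655.

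**What a patient-level count would show in the first row.** About 34 of 172 PM01183 progressions and 0 of 189 control progressions are re-dated: 19.8% versus 0%. Wilson limits are 14.5% to 26.4% and 0% to 2.0%. Newcombe limits for the difference are 19.8 − √(5.3² + 2.0²) = 14.1 and 19.8 + 6.6 = 26.4 points. The second row gives about 51/172 versus 19/189, with an average interval of 12 to 28 points.

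**Why the existing counts miss it.** Of those 34 patients, about 32 are events under both readers. Each adds one to both sides of "Table 11.3.1.43 Progression type by IRC/IA" and none appears in Table 11.3.1.44. Table 11.3.1.19 takes the earlier date, so in this scenario, where IA is never earlier, it returns the IRC result.

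**The case against.** Several points on the other side stand.

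- Table 11.3.1.16 does show in which arm the PFS distribution moves. In the first scenario the control columns are identical while the PM01183 median goes from 5.8 to 6.2 months, and the two hazard ratios differ. A reader might infer that differential dating by arm would go unseen; that is not so. What is missing is the number of patients behind the shift.
- Log-rank tests on IA and IRC PFS are planned in 6.2. On the arm-versus-arm reading the p-value is legitimate, and the fault is a missing label plus duplication.
- It is tempting to say that the SAP has no per-patient reader data. Listing 16.2.6 has them; they are listed, not summarized.
- It is also tempting to take the row "Subsequent therapy before documented progression" in Table 11.3.1.44 as a count of investigator progressions that the IRC did not confirm. It counts new therapy before documented progression whether or not the investigator had called progression, so by itself it does not identify them.
- The documents give no discordance rate or direction. A delay of exactly one scan, always by the investigator, is a chosen scenario.
- IRC procedures are deferred to the IRC charter, which was not supplied and might include discrepancy reporting.

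These points limit the size of the matter. They do not make any reading of the p-value a measure of agreement.

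**Conclusion.** The point holds as a low-cost improvement to a supportive output. SAP 6.2 assesses concordance through marginal curves, Table 11.3.1.16 adds a p-value whose comparison is undefined, and no planned table gives, by arm, how many patients have discordant progression status or dates.

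The shuffling argument needs no assumption. The 0% rejection rates, hazard ratios and patient counts rest on assumed discordance and show scale only. At 50% later dating in both arms the pooled IRC-versus-IA test does reject (96%), so it is insensitive rather than blind to every shift.

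A reader might go on to infer that the primary result is at risk. The documents do not support that: the primary test is the stratified log-rank on PFS by IRC, and its alpha, power and 332 events do not depend on this table. The conclusion is confined to the SAP, since the IRC charter was not available.

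**What to change.** 1. Delete the log-rank p-value from Table 11.3.1.16. Keep the four columns, medians and overlaid curves as description.
2. Add one patient-level table by arm that cross-classifies IRC and IA progression: both, IA only, IRC only, neither. Give deaths without documented progression by either reader their own row and do not count them as agreement; otherwise each would pass as a match, because such a death is an event on the same date for both readers.
3. Where both readers record progression, classify the IRC date as earlier, same or later. Same means the same scheduled eight-week assessment, derived from the tumor-assessment and IRC date data. Listing 16.2.6 alone is not enough: it holds months and event status, not the visit or the type of event.
4. Report by arm (a) the share of IA progressions not confirmed, or dated later, by the IRC and (b) the share of IRC progressions missed, or dated later, by IA. Give each with the between-arm difference and 95% CI (Newcombe), descriptively.
5. Replace the 6.2 sentence with, for example: *Agreement between IRC and IA on progression status and timing will be tabulated per patient by arm, with between-arm differences in discordance and 95% CIs; Kaplan-Meier curves by reader are descriptive, and the readers will not be compared by log-rank test.*

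The cost is one table shell, one sentence and some derivation work on dates. No new data collection or analysis population is needed.
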